5.3 Removal of Patients from Protocol Therapy

If at any time the constraints of this protocol are detrimental to the patient's well-being, or if the patient is unable to comply with the requirements of the protocol, the patient will be removed from protocol therapy.

5.4 Development of intercurrent medical problems that would make continued protocol therapy detrimental to the patient's safety

If a non-treatment related intercurrent illness is expected to be of limited nature, then treatment may be delayed for more than 2 weeks. In this case, the patient would need to be re-evaluated before resuming protocol therapy.

5.5 Patient chooses to discontinue treatment or follow-up

In this event, the reason(s) for withdrawal will be documented.

The reason(s) for withdrawing the patient from the treatment portion of the study will be documented in the case report form. If available, the following information will be recorded in the case report form: date of disease relapse, date of death, cause of death, and autopsy report.

Section 6.0 Measurement of Effect:

To avoid assay variability which can confound vitamin D determinations a radioimmunoassay method will be used to measure all vitamin D measurements by liquid chromatography-tandem mass spectrometry (LC-MS/MS) (this is the Nebraska Medicine's standard). Calibration used a 6-point standard curve over a concentration range 0-100 ng/mL. This is the preferred test for assessment of vitamin D is serum 25-hydroxyvitamin D (25(OH) D). The reason for this test is because it is minimally influenced by recent dietary intake or recent sun exposure, and it is considered the most accurate functional indicator of vitamin D stores. However, if this method is not available, the method used by the local lab will be acceptable.

Study ranges used:

- <30 is considered inadequate
- 30-80 Adequate

- >150 Potentially toxic vitamin D level

6.1 Toxicity criteria

This trial will assess only the grade 3 and 4 toxicities related to the Vitamin D administration. The NCI Common Toxicity Criteria Adverse Events (CTCAE) Version 4 (Appendix B) will be used to grade toxicity. It is available at the following internet site:

http://ctep.cancer.gov/protocolDevelopment/electronic_applications/ctc.htm#ctc_40

6.2 Survival

Subjects will be analyzed with respect to overall and progression-free survival.

Overall survival is defined as time from study entry until death from any cause. For subjects who are still alive at the time of the study analysis or are lost to follow-up, survival will be censored at the last recorded date that the subject was known to be alive.

Progression-free survival is defined as time from study entry until the first notation of clinical progression, relapse, starting new therapies or death from any cause. For subjects who are still progression-free at the time of the study analysis or are lost to follow-up, progression-free will be censored at the last recorded date that the subject was known to be progression-free.

Response will be determined by the Principal Investigator or the lead site investigators.

Section 7.0 Study Parameters:

	Low Levels <30 ng/mL - RANDOMIZED GROUP					
	Pre-Treatment (within 30 days of Consent)	First Dose	6 months Day 182 (+/- 30 Days)	12 months Day 365 (+/- 30 Days)	Year 2 Day 730 (+/- 30 Days)	Year 3 Day 1095 (+/- 30 Days) End of Study
History & Physical	X					
Height, Weight, Vital Signs	X					
Monitor for Vitamin D related AEs			X	X	X	X
Serum Calcium	X					
Serum 25- hydroxyvitamin D [25(OH) D]	X		X	X	X	X
Vitamin D		X - Daily Dosing at Home for 3 years				
Long-term progression free survival and outcome ¹						X

Normal Level $\geq 30\text{ng/ml}$ - CONTROL GROUP*		
Followed only for long-term progression free survival and outcome. No further evaluation of serum 25-hydroxyvitamin D [25(OH) D] will be obtained. (NOTE: subjects currently taking Vitamin D supplements will be encouraged to continue their supplementation.)		
Required studies	Pre-Treatment (Within 30 days of Consent)	Year 3 - Day 1095 (+/- 180 Days) End of Study
History & Physical	X	
Height, Weight, Vital Signs	X	
Serum Calcium	X	
Serum 25-hydroxyvitamin D [25(OH) D]	X	
Long-term progression free survival and outcome ¹		X

¹ Progression defined as relapse, progression, or starting new therapies, or death

Section 8.0 Drug Formulation and Procurement (per UNMC Lexicomp Online):

8.1 Clinical Overview

Vitamin D (Natural Products Database)

Common Name(s): Sunshine vitamin; Vitamin D

8.1.1 Uses

Vitamin D, long recognized as playing a role in bone and calcium homeostasis, is being investigated for use in cardiovascular disease, cancer, diabetes, infections, multiple sclerosis, psoriasis, respiratory health, and other conditions. More clinical trials are needed.

8.1.2 Dosing

The American Academy of Pediatrics recommends 400 units/day of vitamin D in infants and adolescents. Clinical data are not yet sufficiently robust to make definitive recommendations for therapeutic dosages of vitamin D; however, in the elderly, 700 to 1,000 units/day have been shown to reduce the risk of falls.

8.1.3 Contraindications

Contraindications have not been identified.

8.1.4 Pregnancy/Lactation

Routine use of supplemental vitamin D during pregnancy is not supported by safety evidence. However, adequate maternal intake of vitamin D-containing foods during lactation ensures that breast-fed infants receive sufficient vitamin D.

8.1.5 Interactions

The use of statins has been shown to increase serum vitamin D levels. Corticosteroids decrease the metabolism of vitamin D and orlistat reduces its absorption; phenobarbital and phenytoin increase the hepatic metabolism of vitamin D.

8.1.6 Adverse Reactions

High doses of vitamin D have rarely produced adverse events in clinical trials.

8.1.7 Toxicology

Toxicity due to vitamin D is considered to manifest at serum levels greater than 150 ng/mL of 25-hydroxyvitamin D. Symptoms of hypervitaminosis D include fatigue, nausea, vomiting, and weakness associated with hypercalcemia. (Page 27 sites more toxicity details)

8.1.8 Source

Vitamin D3 (cholecalciferol) is synthesized in the skin by transformation of 7-dehydrocholesterol exposed to ultraviolet B rays of the midday sun. Vitamin D binding protein transports D3 to the liver, where it is hydroxylated to the inactive 25-hydroxyvitamin D form (caldiol). In the kidneys, it is further hydroxylated by the enzyme 1-alpha-hydroxylase to active 1, 25-dihydroxyvitamin D (calcitriol).^{Ref}

Vitamin D as ergocalciferol (vitamin D2) is found in some plants and in salmon, sardines, mackerel, tuna, cod liver oil, shiitake mushrooms, egg yolk, and fortified foods.^{Ref} Deficiency may result from decreased absorption (such as in cystic fibrosis, celiac and Crohn diseases, and drug interactions), increased catabolism (caused by anticonvulsant and antiretroviral therapy and some immunosuppressant drugs), and hepatic and renal failure, as well as from inadequate intake.^{Ref}

8.1.9 Chemistry

Vitamin D is a hormone precursor and acts to control calcium absorption in the small intestine. It affects parathyroid hormone, which in turn affects the metabolism of skeletal mineralization and calcium homeostasis in the blood. Additionally, effects on cytokines and immune-modulating effects are reported.^{Ref}

The accepted biomarker is 25-hydroxyvitamin D (or caldiol). Only in advanced renal disease are measurements of 1, 25-dihydroxyvitamin D (calcitriol) relevant.^{Ref} Concern over standardization of assays exists.^{Ref}

8.2 Uses and Pharmacology

8.2.1 Cancer

8.2.1.1 Animal data

Preclinical studies have shown an effect of vitamin D on a variety of cancer cell lines. Cell cycle interruption, apoptosis, and other mechanisms have been demonstrated.^{Ref}

8.2.1.2 Clinical data

Meta-analyses of observational studies suggest a lower incidence of cancer with higher vitamin D serum levels.^{Ref} Particular attention has focused on breast, colon, and prostate cancer. In the Women's Health Initiative study, no association was found between vitamin D and breast cancer^{Ref} while the Health Professionals Follow-Up Study suggested a decreased risk of cancer with increasing 25-hydroxyvitamin D levels.^{Ref} In a meta-analysis evaluating the effects of vitamin D supplementation on overall mortality risk, a subgroup analysis (n = 13 in studies) of long-term vitamin D supplementation for at least 3 years revealed a significant reduction in cancer mortality (relative risk [RR] = 0.88; 95% confidence interval [CI], 0.79 to 0.98).^{Ref}

The American Society of Clinical Oncology clinical practice guideline adaptation for the screening, assessment, and management of fatigue in adult survivors of cancer (2014) notes that results from small pilot studies on the effectiveness of supplements, such as vitamin D, for managing cancer-related fatigue are equivocal (inconclusive).^{Ref}

8.2.2 Cardiovascular

Vitamin D is thought to exert cardiovascular effects by a number of mechanisms, including effects on the renin-angiotensin-aldosterone system, homeostasis of calcium, and secondary effects on hyperparathyroidism and insulin resistance.^{Ref}

8.2.2.1 Animal data

Available data from large clinical trials make animal data largely redundant.

8.2.2.2 Clinical data

No clinically important effect on coronary or cerebrovascular risk or outcomes was found with vitamin D and calcium supplementation over 7 years in the Women's Health Initiative randomized trial.^{Ref} Other systematic reviews of clinical trials have largely found no effect of vitamin D supplementation on cardiovascular outcomes and hypertension.^{Ref} Based on limited trial data in populations with vitamin D insufficiency, moderate to high doses of vitamin D increase the serum vitamin D metabolite status and may reduce cardiovascular risk; however, further studies are required before a definitive place in therapy can be established.^{Ref} In a meta-analysis evaluating the effects of vitamin D supplementation on overall mortality risk, a subgroup analysis (n = 13 in studies) of long-term vitamin D supplementation for at least 3 years revealed no reduction in cardiovascular mortality.^{Ref}

8.2.3 Diabetes

8.2.3.1 Animal data

Animal studies suggest vitamin D exerts effects on the homeostasis of glucose metabolism, as supplementation in animals has led to decreases in plasma glucose.^{Ref} A direct effect on insulin

secretion has been suggested, as well as effects on insulin receptor expression, insulin sensitivity, and direct action on insulin itself.^{Ref}

8.2.3.2 Clinical data

Epidemiological data support a role of vitamin D in reducing the incidence of diabetes. Vitamin D supplementation in infants has been associated with a decreased risk of type 1 diabetes, and a meta-analysis has demonstrated an association between low vitamin D status and the prevalence of type 2 diabetes or metabolic syndrome.^{Ref} However, limited, small studies have shown equivocal results on the impact of vitamin D on serum glucose.^{Ref} A 12-month, double-blind, randomized controlled trial (n = 86) in adults with type 2 diabetes mellitus and vitamin D deficiency (median, 11.9 ng/mL), found that vitamin D supplementation (1,904 units/day) for 6 months did not significantly affect blood glucose, insulin levels, HbA_{1c}, systolic blood pressure, or body weight. However, a significant correlation was observed between vitamin D levels and HbA_{1c} with the lowest HbA_{1c} occurring at less than 20 ng/mL.^{Ref} Similar results were seen in another double-blind randomized clinical trial conducted in 158 Koreans with type 2 diabetes and vitamin D deficiency or insufficiency who supplemented their diet with 2,000 units/day of vitamin D3 plus calcium for 24 weeks. Neither glycemic control nor HbA_{1c} were significantly different in patients treated with vitamin D plus calcium compared with those treated with only calcium supplementation.^{Ref} Interestingly, in a meta-analysis evaluating the effects of vitamin D supplementation on overall mortality risk, a subgroup analysis (n = 13 in studies) of long-term vitamin D supplementation for at least 3 years revealed a reduction in mortality only when vitamin D plus calcium was compared with placebo but not when compared with calcium, and not when vitamin D alone was compared with placebo. Other long-term subgroup benefits appeared in patients younger than 80 years, with a dose of 800 units or less, and in patients with a baseline 25-hydroxyvitamin D level less than 50 nmol/L. The meta-analysis primary outcome (n = 42 intervention randomized clinical trials; N = 85,466 patients) identified a decrease in all-cause mortality when vitamin D supplementation was continued for 3 years or longer ($P = 0.001$); heterogeneity was insignificant.^{Ref}

As a component of medical nutrition therapy for patients with type 1 or type 2 diabetes, the American Diabetes Association Standards of Care (2014 and 2015) does not support routine supplementation with micronutrients such as vitamin D to improve glycemic control (low-quality evidence).^{Ref}

8.2.4 Infectious disease

Vitamin D receptors are ubiquitous in the body and are found in immune system-related cells, such as B and T lymphocytes, neutrophils, and macrophages. An emerging role is being described for vitamin D in immune response.^{Ref}

The Randomized Evaluation of Calcium or Vitamin D (RECORD) trial investigated the effect of vitamin D supplementation (800 units/day) on self-reported infections and antibiotic use but did not find a statistically significant association.^{Ref} A single dose of vitamin D demonstrated an enhanced immune response in a randomized clinical trial in tuberculosis patients^{Ref} while a systematic review of clinical trials evaluating the effect of vitamin D supplementation (largely in

tuberculosis, influenza, and other viral infections) concluded that further studies are warranted.^{Ref}

Despite a significant increase in serum 25-hydroxyvitamin D, the recurrence of bacterial vaginosis in women being treated at an urban sexually-transmitted disease clinic was not significantly reduced by vitamin D supplementation (50,000 units × 9 doses) over 24 weeks. The trial was a randomized, placebo-controlled, double-blind study (N = 118).^{Ref}

8.2.5 Multiple sclerosis

Theoretical and epidemiological models support a place in therapy for vitamin D in multiple sclerosis. An inverse relationship has been demonstrated between vitamin D levels and multiple sclerosis, especially in patients younger than 20 years of age, while the development of multiple sclerosis in women has been associated with low 25-hydroxyvitamin D levels. Lower serum vitamin D and severity of multiple sclerosis, as well as incidence of relapses, has also been demonstrated.^{Ref}

Little prospective data exist; however, a small clinical study (N = 12) showed a decrease in the number of lesions with magnetic resonance imaging with administration of 1 mg (40,000 units) daily over 28 weeks.^{Ref} No serious adverse events were reported at this dosage, and no hypercalcemia or hypercalciuria was reported.

8.2.6 Renal

8.2.6.1 Animal data

Available data from large clinical trials make animal data largely redundant.

8.2.6.2 Clinical data

As kidney function is impaired, the inability to maintain adequate phosphorus and calcium levels results in compensatory mechanisms involving parathyroid hormone. Resultant increases in bone metabolism to release calcium to the system cause bone deformation, pain, and an increased risk of fractures. Supplementation of vitamin D suppresses parathyroid hormone, but it may also slow the progression of chronic kidney disease via novel pathways. Vitamin D analogs, such as paricalcitol, may exert anti-inflammatory effects, as well as affect the renin-angiotensin systems and decrease morbidity and mortality. However, studies are limited.^{Ref} A randomized, double-blind trial in chronic dialysis patients (n = 50) observed no improvement in cardiac function as measured by 24-hour blood pressure, arterial stiffness, and cardiac function in patients treated for 6 months with 75 mcg (3,000 units) or placebo. Although, left ventricular end-diastolic function was increased significantly in the treatment group ($P = 0.024$).^{Ref}

8.2.7 Other uses

8.2.7.1 Alopecia

The role of vitamin D and its receptors is not well understood, but the potential for topical calcitriol to upregulate the receptors has been evaluated in animal models of chemotherapy-

induced alopecia. Hair loss is not prevented; however, hair regrowth over the entire animal has been demonstrated.^{Ref} Limited clinical studies have produced varying results, possibly dependent on the chemotherapeutic agent.^{Ref}

8.2.7.2 Atopic eczema/dermatitis

A 2012 Cochrane review identified 2 randomized clinical trials evaluating vitamin D for atopic eczema/dermatitis that met criteria for analysis. Vitamin D supplementation alone did not provide significant benefit over placebo in any of the primary, secondary, or tertiary outcomes. However, vitamin D (cholecalciferol 1,600 units) and E (600 units alpha-tocopherol) combination therapy resulted in a significant difference in severity scores at the end of 60-day treatment, as well as improvement in dryness, pruritis, and erythema compared with placebo in 52 adults and children older than 13 years of age.^{Ref}

8.2.7.3 Dementia/Depression

Observational studies and animal models suggest a role for vitamin D in treating dementia. Vitamin D exerts antioxidant effects, and receptors are found in the human cortex and hippocampus. Correlations between the Mini-Mental State Examination scores and vitamin D serum levels, as well as global cognitive function, have been shown.^{Ref} One clinical trial demonstrated an improvement in mild depression with vitamin D supplementation.^{Ref}

8.2.7.4 Falls in the elderly

Systematic reviews have been conducted on the effects of supplemental vitamin D and the risk of falls in the elderly.^{Ref} Low doses (200 to 600 units/day) showed no effect, while higher doses (700 to 1,000 units/day) reduced the risk of falling in the elderly by 19% to 22%.^{Ref}

8.2.7.5 Mortality

A meta-analysis of 32 studies published and indexed between 1966 and 2013 evaluated the relationship between vitamin D (25-hydroxyvitamin D) and all-cause mortality in healthy participants as well as patients in clinic cohorts. The age-adjusted death rate in individuals with vitamin D levels in the lowest quantile (0 to 9 ng/mL) was almost twice that of those in the highest quantile (more than 35 ng/mL). The pooled dose-response curve declined steeply between 0 and 30 to 39 ng/mL and flattened at greater than 50 ng/mL, with all-cause mortality being significantly higher when levels were up to 30 ng/mL ($P < 0.01$).^{Ref}

8.2.7.6 Psoriasis

Topical synthetic vitamin D (eg, tacalcitol) may be an alternative to topical steroids and may inhibit keratinocyte proliferation, as well as influence immune modulation.^{Ref}

8.2.7.7 Respiratory health

Vitamin D appears to be capable of inhibiting the pulmonary inflammatory response and enhancing pulmonary defense against pathogens. Population-based studies support an association between circulating vitamin D levels and lung function.^{Ref} The use of vitamin D in

cystic fibrosis is based on knowledge of vitamin insufficiency due to pancreatic insufficiency; however, evidence of benefit is lacking for vitamin D supplementation despite routine use.^{Ref} Addition of high-dose vitamin D3 (100,000 units for 1 dose, then 4,000 units/day x 28 weeks) to inhaled corticosteroid therapy (ciclesonide 320 mcg/day) in adults with symptomatic asthma and low vitamin D3 levels who failed previous treatment, did not significantly alter the rate of first treatment failure or overall treatment failure.^{Ref}

8.2.7.8 Dosing

Clinical response to vitamin D does not always correspond with serum levels of the markers.^{Ref} Generally, a serum level of less than 20 ng/mL of 25-hydroxyvitamin D constitutes a deficiency in adults and children.^{Ref}

The American Academy of Pediatrics recommends 400 units/day vitamin of D in infants and adolescents.^{Ref}

To maintain a serum 25-hydroxyvitamin D level of 25 ng/mL, independently living elderly adults required vitamin D 7.9 to 42.8 mcg daily in a clinical study^{Ref} (20 mcg is equivalent to 800 units).^{Ref} Data from clinical studies are not yet sufficiently robust to make definitive recommendations for therapeutic dosages of vitamin D; however, in the elderly, 700 to 1,000 units/day have been shown to reduce the risk of falls.^{Ref}

8.2.7.9 Pregnancy/Lactation

The safety and efficacy of vitamin D in pregnancy has not been confirmed. Clinical trials have evaluated the excretion of vitamin D in breast milk by mothers given supplementation. Adequate levels of vitamin D are achieved in breast-fed infants from mothers with a vitamin D intake of 400 units/day. All milk formulas sold in the United States contain at least 400 units/L of vitamin D.^{Ref}

8.3 Interactions

The use of statins has been shown to increase serum vitamin D levels.^{Ref} Corticosteroids decrease the metabolism and orlistat reduces absorption of vitamin D, while phenobarbital and phenytoin increase the hepatic metabolism of vitamin D.^{Ref}

8.4 Adverse Reactions

High doses of vitamin D have rarely produced adverse events in clinical trials.^{Ref}

Apart from the obvious hazards, prolonged sun exposure alone cannot cause vitamin D overdose because sunlight destroys excess vitamin D3.^{Ref}

8.5 Toxicology

Toxicity due to vitamin D is considered to manifest at levels greater than 150 ng/mL of serum 25-hydroxyvitamin D. Symptoms of hypervitaminosis D include fatigue, nausea, vomiting, and weakness associated with hypercalcemia.^{Ref} Reports of toxicity exist for children administered

high-dose vitamin D after World War II in Europe. Hypercalcemia, nephrocalcinosis, adverse cardiovascular effects, early aging, and premature death were reported.^{Ref}

Hypervitaminosis D in 2 young brothers was reported subsequent to an overdose of an OTC vitamin D supplement that resulted from 2 simultaneous dosing errors; the OTC product (Merluzzovis cod liver oil-based capsules) contained approximately 1,000 times the labeled vitamin D content per capsule, and the mother administered twice the dose as recommended on the label. After 1 month of supplementation, the 12-year-old had received a total of 7,632,000 units (254,490 units/day instead of the recommended 400 units/day) and was hospitalized for abdominal pain, constipation, vomiting, hypercalcemia, suppressed parathyroid, and acute renal failure. The 15-year-old brother had received a total of 3,180,000 units over the previous 2 weeks, was asymptomatic, normocalcemic, and had normal renal function. Their vitamin D levels were well over the toxic lower limit (150 ng/mL) and were 535 ng/mL and 484.9 ng/mL, respectively. The 12-year-old was normocalcemic and had normal renal function within 1 month of discharge.^{Ref}

This product may adversely interact with certain health and medical conditions, other prescription and over-the-counter drugs, foods, or other dietary supplements. This product may be unsafe when used before surgery or other medical procedures. It is important to fully inform your doctor about the herbal, vitamins, mineral or any other supplements you are taking before any kind of surgery or medical procedure. With the exception of certain products that are generally recognized as safe in normal quantities, including use of folic acid and prenatal vitamins during pregnancy, this product has not been sufficiently studied to determine whether it is safe to use during pregnancy or nursing or by persons younger than 2 years of age.

Section 9.0 Toxicity Reporting Guidelines:

This protocol will comply with monitoring and adverse event reporting requirements of the UNMC/Fred & Pamela Buffett Cancer Center Data Monitoring plan. The protocol will adhere to the institutional and FDA guidelines for the toxicity reporting.

Grade 3 and 4 adverse events (AEs) related to the Vitamin D administration will be graded according to the National Cancer Institute Common Terminology, Criteria for Adverse Events (NCI-CTCAE), version 4.0, which can be accessed at the following URL.

http://ctep.cancer.gov/protocolDevelopment/electronic_applications/ctc.htm#ctc_40

The over the counter agent used in the protocol is commercially available with a well-characterized toxicity profile.

All subjects will be closely followed for grade 3 and 4 toxicity/adverse events related to the Vitamin D administration from the time that the first dose of study drug is administered and ending 30 days following the final therapy. Adverse events will be assessed by reports from subjects of Vitamin D related grade 3 or higher adverse events to their physician-investigators, standard laboratory results and by physical examinations. Vitamin D related Only **prescription** medication taken to relieve symptoms of the Vitamin D related AE will be recorded in addition to the outcome. All other/routine concomitant medications WILL NOT be recorded. Deaths occurring within 30 days of study treatment regardless of relationship will be reported to the UNMC DSMC. Only fatal AEs will be reported to the UNMC IRB per the IRB's policy and procedures.

In addition to complying with all applicable regulatory reporting laws and regulations, vitamin D related serious adverse events and toxicities for all subjects will be reported to the University of Nebraska Medical Center, Institutional Review Board (IRB) and Fred & Pamela Buffett Cancer Center Data and Safety Monitoring Committee (DSMC) and the FDA (if applicable).

9.1 Adverse Experiences Definitions:

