9.2.1 IRB Reporting

All Vitamin D related internal serious adverse events (SAEs) must be reported to the local IRB promptly per institutional human research protection program policies.

9.2.2 Fred & Pamela Buffett Cancer Center Data and Safety Monitoring Committee (DSMC) Reporting

All Vitamin D related adverse events grade 3 or higher (expected or unexpected) will be reported to the University of Nebraska Medical Center, Fred & Pamela Buffett Cancer Center Data and Safety Monitoring Committee (DSMC) in accordance with DSMC guidelines.

In its initial review, the DSMC will make a recommendation for the frequency of DSMC monitoring based on an assessment of risk associated with study-associated therapy, per the DSMC policy.

Detailed policy and procedures for this section may be reviewed at:

<http://www.unmc.edu/cancercenter/clinical/prms.html>

Attribution of AE: The likelihood of relationship of the AE to the study drugs will be determined by the investigator based on the following definitions:

- **Not Related:** The subject was not exposed to the study treatment or another cause is obvious.
- **Probably Not Related:** The AE is most likely explained by another cause, and the time of occurrence of the AE is not reasonably related to the study treatment.
- **Possibly Related:** Study treatment administration and AE occurrence reasonably related in time, and the AE is explained equally well by causes other than study treatment, or treatment administration and AE occurrence are not reasonably related in time, but the AE is not obviously a result of other causes.
- **Probably Related:** Study treatment administration and AE occurrence are reasonably related in time, and the AE is more likely explained by study treatment than by other mechanisms.
- **Definitely Related:** There occurrence and timing of the AE are clearly attributable to the study treatment.

Severity Grade of AE. The severity of events reported on the AE case report form will be determined by the principal investigator according the NCI Common Toxicity Criteria (CTC version 4.0). Copies of the AE report will be submitted to the IRB as indicated in Section 9.1.1.

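### Section 9.0 limits IRB reporting to fatal adverse events, which contradicts its own next paragraph and Section 9.2.1 on non-fatal vitamin D related SAEs

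*Combined protocol and SAP*

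**What the plan says.** Four statements bear on what goes to the IRB.

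- **Section 9.0, opening text.** After a sentence on deaths, "Deaths occurring within 30 days of study treatment regardless of relationship will be reported to the UNMC DSMC", the plan states: "Only fatal AEs will be reported to the UNMC IRB", under that board's own policy.
- **Section 9.0, next paragraph.** "vitamin D related serious adverse events and toxicities for all subjects will be reported to the University of Nebraska Medical Center"; the sentence goes on to name that institution's IRB, the DSMC and, if applicable, the FDA. It has no limit to fatal events and gives no timing.
- **Section 9.2.1 (IRB Reporting).** "All Vitamin D related internal serious adverse events (SAEs) must be reported to the local IRB promptly", under institutional human-subjects policy.
- **Section 9.2.2, closing sentence on severity grading.** "Copies of the AE report will be submitted to the IRB as indicated in Section 9.1.1".

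Two other sections set the context. Section 9.1.2 defines a vitamin D related SAE by six criteria, of which death is one. Section 9.2.2 sends every related event of grade 3 or higher to the DSMC.

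**The concern.** The restrictive sentence in Section 9.0 carries no qualifier. Taken at face value, it removes every non-fatal event from IRB reporting, including the related SAEs that the next paragraph and Section 9.2.1 require to be reported.

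The IRB reviews whether the risk to participants remains acceptable and whether the consent information is still adequate. The plan makes reporting to it a separate duty (9.2.1) from reporting to the DSMC (9.2.2). If staff followed the restrictive sentence, the IRB would not be told of serious non-fatal harm attributed to the study supplement. Section 12.10 names hypercalcemia as a possible toxicity, so a non-fatal hospitalisation for related hypercalcemia is a realistic example.

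**Working it through.** This is a comparison of text. No sample size, power or error rate enters, and the plan gives no figure to reproduce.

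**Step 1: can an SAE be non-fatal?** Section 9.1.2 lists death, life-threatening event, hospitalisation, disability or incapacity, congenital anomaly and important medical event. Removing death leaves 6 − 1 = 5 criteria that an event can meet without being fatal.

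**Step 2: one test case under each rule.** Take a vitamin D related, non-fatal hospitalisation. It is serious under 9.1.2.

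| Place | Scope stated for the IRB | Test case goes to the IRB? |
|---|---|---|
| 9.0, opening text | fatal AEs only | No |
| 9.0, next paragraph | related SAEs and toxicities, all subjects | Yes |
| 9.2.1 | all related internal SAEs | Yes, promptly |
| 9.2.2, closing sentence | refers to 9.1.1 | No rule found |

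**Step 3: is it the same board?** The restrictive sentence names the UNMC IRB and 9.2.1 names the local IRB, so those two alone might concern different boards. The second paragraph of 9.0 names the UNMC IRB, however, so the contradiction exists for one board within one section.

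**Step 4: does the cross-reference settle it?** Section 9.1.1 defines a vitamin D related adverse event and contains no IRB reporting rule. A reader who follows the pointer from 9.2.2 gets no answer.

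**Step 5: do the two broader rules agree?** On related SAEs, yes. They differ at the edges: 9.0 adds toxicities that need not be serious, while 9.2.1 adds the requirement of promptness and the word internal. The conflict on SAEs is therefore one sentence against two concordant ones, with a secondary difference over toxicities.

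**Step 6: where else does the event go?** The second paragraph of 9.0 sends related SAEs to the DSMC as well, and 9.2.2 sends it related events of grade 3 or higher.

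**Step 7: who is exposed?** Section 10.1 plans 70 patients in each randomized arm, so 70 + 70 = 140 patients taking study vitamin D. Section 5.2 has them dosed daily for three years. This is the population to which the rules apply and not an estimate of affected events.

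**The case against.** The strongest answer is that the sentence only sorts the deaths just mentioned. The sentence before it sends all deaths within 30 days to the DSMC, whatever their cause. Section 9.1.1 ties a vitamin D related adverse event to a possible causal link. On that reading, the restrictive sentence says that only deaths that are adverse events in this sense also go to the IRB, and the next paragraph then deals with related SAEs. A coordinator who sent nothing would have to overlook both that paragraph and the subsection devoted to IRB reporting. This reading is plausible and may be what was meant, but the sentence contains no words confining it to deaths. The IRB policy it cites might settle the matter; that policy is not in the documents, and 9.2.1 also appeals to institutional policy while stating a wider scope.

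A second answer is that oversight does not depend on the IRB alone. This stands in part. The DSMC receives these events, Section 9.3 provides for audit at least semi-annually and scientific review at least annually, and Section 10.4.1 has a stopping rule for related severe events. None of these replaces the separate IRB duty.

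Two stronger inferences should be resisted. A reader might conclude that non-fatal serious harm would escape all oversight; the DSMC route in 9.0 and 9.2.2 contradicts that. A reader might also conclude that UNMC and affiliate sites will report the same event differently. The documents do not say which board serves the affiliates or how sites have read the text, so that is conjecture.

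**Conclusion.** The contradiction is real and lies in the current text. For a non-fatal vitamin D related SAE, one sentence in Section 9.0 gives the opposite answer to the following paragraph and to Section 9.2.1. The consequence is limited to this: such an event could go unreported to the IRB if the restrictive sentence is followed as written.

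Its size can be stated only by scope. Five of the six seriousness criteria are affected, in a planned 140 treated patients. The number of events cannot be estimated from the documents; Section 8.4 describes adverse events at high doses as rare in trials, and Section 12.10 calls toxicity rare. It would overstate the matter to speak of several mutually incompatible rules, because the two broader statements agree on SAEs.

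This is an internal inconsistency in safety reporting and should be corrected. Confidence is high on the textual conflict and lower on whether any report would be missed, since that depends on how sites read the text and on an IRB policy that is not supplied. The wrong pointer in 9.2.2 is an editorial error that leaves the conflict unresolved but adds no separate safety weight.

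**What to change.** 1. Delete the restrictive sentence in Section 9.0, or reword it so that it covers only which deaths go to the IRB and cannot override the SAE rule.
2. State one IRB reporting rule in Section 9.2.1, checked against the governing IRB policy. It should say which events go to which board and when, and whether the toxicities mentioned in the second paragraph of 9.0 are included.
3. Have Section 9.0 refer to 9.2.1 instead of stating its own scope.
4. Correct the pointer in 9.2.2 from Section 9.1.1 to Section 9.2.1.

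Limiting the restrictive sentence to deaths unrelated to vitamin D would not be a sound repair. The plan sends those deaths to the DSMC, and no passage supports a duty to send them to the IRB.

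The cost is wording in an amendment and a short notice to sites. It adds no IRB reports beyond those that the second paragraph of 9.0 and Section 9.2.1 already require, and it leaves treatment, endpoints and analysis unchanged.
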